The ADVOR trial will evaluate whether adding a low cost medication (Diamox ® 8.28 € public price/vial) on top of the standard treatment will reduce the hospital stay of admitted HF patients with 25% as well as reduce the need for renal replacement strategy. In daily practice this would result in an additional cost of < 20€ to potentially reduce the average cost with at least 2500 € per hospitalised patient. This would also imply that acetazolamide, on top of usual care, has the potential to result in a direct cost saving of 38.203.690 € in Belgium (=25% reduction on the budget actually spent on HF hospitalization).

Additionally, it's estimated that a more thorough successful decongestion will also lead to a reduction in heart failure rehospitalisation of 25% thereby further reducing health care cost. Therefore, a positive result of the ADVOR trial and wide adaptation of the therapeutic algorithm might translate into a reduction in expenses directly related to 1) a shorter hospitalization duration, 2) less costly 'majeur or extreem' HF, and 3) less HF hospitalizations.

While these estimations might be considered 'very optimistic', they are merely a reflection of the potential impact of a reduction of hospitalisation duration as well as readmission seen in the Ziekenhuis Oost Limburg AV after implementation of the aforementioned care pathways including a better and faster decongestion with acetazolamide. However, assuming that the primary endpoint is reached (25% decongestion in the treatment group vs 15% in the standard of care), this would translate in a 11.7% relative risk reduction. If this would translate into a 11,7% reduction in heart failure related expenditure, an annual considerable cost-saving of 17.880.408 € might still be reached.

Importantly, due to the off-patent status of the drug tested in ADVOR there will never be an industry sponsored trial to support this hypothesis. Therefore, ADVOR will lead to a revival of a "forgotten" medicine because it has the potential to significantly impact the way we treat congestion in heart failure patients.

Finally, it's expected that ADVOR will result in a novel innovative approach of treatment of decompensated HF which is focused at a different level of the nephron to achieve better, easier and safer decongestion. In that way ADVOR might pave the way towards a complete change in thinking with regards to treating decompensated heart failure.

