4.1.3 Secondary objectives and endpoints

Secondary Objectives	Secondary Endpoints

To investigate if combination therapy with acetazolamide:
 
 - leads to improved clinical outcome in decompensated HF (less HF readmissions, lower all-cause mortality) - shortens the length of stay in patients with decompensated HF, which is expected to reduce health care expenditure - leads to improved quality of life 	
 - Combined endpoint of all-cause mortality and HF readmission during 3 months of follow-up - Length of index hospital admission - Change in EuroQoL

Definition of secondary endpoints

- The combined endpoint of all-cause mortality and HF readmission during 3 months of follow-up is a binary endpoint. The time to the combined endpoint will be calculated as the time between start of study medication (day 1) and the date of (first) HF readmission or mortality (whichever comes first). *HF readmission* is defined as either a hospital admission or an unscheduled contact at the emergency department and when

treatment with intravenous loop diuretics is initiated because of worsening HF.

- Length of index hospital admission (calculated in days) is obtained as the date of discharge from the hospital minus the date of screening +1.
- EuroQol is a five dimension patient-reported QoL questionnaire (EQ-5D-5L). The EQ-5D-5L health states, defined by the EQ-5D-5L descriptive system, are converted into a single index value (<https://kce.fgov.be/nl/een-belgische-waardenset-voor-de-eq-5d-5l-%E2%80%93-hoe-gezondheidsgerelateerde-levenskwaliteit-waarderen>). The VAS assessment of the EQ-5D will also be used. The EQ VAS records the patient's self-rated health on a vertical visual analogue scale.

The index values and EQ-VAS at baseline, the morning of day 4 or discharge (whatever comes first), and at 3 months of follow-up will be used for the secondary objective.

During the study the baseline EQ-5D-5L questionnaire has been completed as soon as possible after screening up to day 1.

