4.1.4 Safety objectives and endpoints

Safety Objective	Safety Endpoints
To evaluate the safety of the combination therapy with acetazolamide in this patient population.	
 - Severe metabolic acidosis at any time during study treatment - Doubling or more ($\geq 2x$) of baseline serum Creatinine, or $\geq 50\%$ decrease in baseline eGFR at any time during study treatment - Hypokalaemia at any time during study treatment - Hypotension at any time during study treatment

Definition of Safety endpoints

- Severe metabolic acidosis: a value of bicarbonate < 12 mmol/L at any time during study treatment (day 1- day 4)
- Worsening of eGFR or the need for renal replacement therapy during the index hospitalization. eGFR is obtained via the CKD-EPI formula. The eGFR values will be calculated (in mL/min/1.73 m²) from the local laboratory creatinine measurements using the CKD-EPI formula (Levey et al 2009)².
- Hypokalaemia: a value of potassium $\leq 3,0$ mmol/L at any time during study treatment (day 1- day 4)
- Hypotension: a value of systolic blood pressure < 85 mmHg at any time during study treatment (day 1- day 4)

Baseline laboratory value

For all laboratory variables, the baseline value is defined as the last value prior to the first dose of study drug.

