4.1.5 Exploratory objectives and endpoints

Exploratory Objectives	Exploratory endpoints
To determine whether acetazolamide compared with placebo in combination with loop diuretics will have an effect on body weight.	Change in body weight.
To determine whether acetazolamide compared with placebo in combination with loop diuretics will reduce the incidence of all cause rehospitalisation's.	All cause rehospitalisation during first 3 months after study start dose.
To determine whether acetazolamide compared with placebo in combination with loop diuretics will have an effect on total urinary volume and natriuresis.	Total urinary volume and natriuresis starting from first intravenous (IV) diuretic administration at randomization until the morning of day 3.
To determine whether acetazolamide compared with placebo in combination with loop diuretics will have an effect on plasma natriuretic peptides.	Change in plasma natriuretic peptides change from screening until day 4 or at discharge (whatever comes first) and at 3 months follow up visit.
To determine whether acetazolamide compared with placebo in combination with loop diuretics will have an effect on the total dose of IV loop diuretics used during first 4 days.	Total dose of IV loop diuretics used during first 4 days.
Effect of decongestion on uptitration of neurohormonal blockers	Changes in doses of neurohumoral blockers.
To determine whether acetazolamide compared with placebo in combination with loop diuretics will reduce the need for renal replacement therapy.	Need for renal replacement therapy or ultrafiltration during first 3 months after study start dose.
To determine whether acetazolamide compared with placebo in combination with loop diuretics will reduce the incidence of hyponatremia during treatment phase.	Hyponatremia during treatment phase.
To evaluate if liver dysfunction at screening has an effect on the treatment effect on the primary endpoint.	Liver dysfunction at screening and primary endpoint.
To determine whether acetazolamide compared with placebo in combination with loop diuretics will have an effect on plasma volume changes during treatment phase.	Change in plasma volume during treatment phase (assessed by albumin and hematocrit)

Exploratory Objectives	Exploratory endpoints
To evaluate if iron deficiency at screening has an effect on the treatment effect on the primary endpoint	Iron deficiency at screening and primary endpoint

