5.12 Analysis of safety outcomes

For the safety endpoints, all patients that were randomized and received at least 1 dose of the investigated drug or placebo will be included. For the safety analysis, patients will be grouped based on the actual study treatment received.

The safety outcomes are all binary outcomes. For descriptive purposes, the number (%) of failure and success for each safety outcome will be given per treatment arm.

For each safety outcome, the treatment effect will be evaluated by means of a generalized linear mixed model (logistic model). The statistical model will include a fixed treatment effect, and a random centre effect. The results of this model will be presented as an odds-ratio (OR), 95% confidence interval and the associated p value.

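### SAP v2.0 section 4.1.4 gives the renal safety endpoint two incompatible definitions, and one counts renal replacement therapy only until discharge, which acetazolamide is hypothesised to bring forward

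*Combined protocol and SAP*

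**What the plan says.** SAP v2.0 section 4.1.4 presents the safety endpoints first as a table and then as definitions.

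- **Table, renal row:** at least a doubling of serum creatinine, or at least a 50% "decrease in baseline eGFR at any time during study treatment". RRT is not mentioned.
- **Definition, renal bullet:** "Worsening of eGFR or the need for renal replacement therapy during the index hospitalization". This adds RRT, replaces the treatment period with the hospital stay, and does not repeat the table's thresholds.
- **The other three definitions** (acidosis, hypokalaemia, hypotension) are fixed at days 1 to 4.

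Length of stay is itself an outcome. SAP section 4.1.3 asks whether acetazolamide "shortens the length of stay in patients with decompensated HF". Protocol v2.0 section 10.4 says the trial will evaluate whether the drug "will reduce the hospital stay of admitted HF patients with 25% as well as reduce the need for renal replacement strategy". SAP section 5.12 analyses every safety outcome as binary in a logistic mixed model with treatment and a random centre effect, and with no term for time at risk.

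RRT also appears in SAP section 4.1.5 as an exploratory endpoint over a fixed period: "Need for renal replacement therapy or ultrafiltration during first 3 months after study start dose".

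**The concern.** There are two linked problems. First, the table and the definition disagree on both the window and the content of the same endpoint, so the SAP does not settle what will be counted.

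Second, if the definition governs, the RRT part is counted until a date that treatment is meant to bring forward. A patient who starts dialysis on day 11 is an event if still in hospital and not an event if discharged on day 9. If acetazolamide shortens stay as hoped, its patients are counted for fewer days, and the logistic model does not correct for that. Kidney harm is a natural safety question when a second diuretic is added. The result labelled as safety could lean towards acetazolamide with no renal benefit behind it.

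**Working it through.** **Inputs from the documents**

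- Reference stay: 12 days, the 2014 national average (Protocol v2.0 section 10.4, which also gives 17.55 days for advanced symptoms and 9.12 days for severe patients at the sponsor's hospital).
- Hypothesised shortening: 25% (same section), so 12 × 0.75 = 9 days.
- Patients: 519, allocated 1:1, so 519 / 2 = 259.5 per arm (SAP sections 4.5 and 4.3.4).

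**Assumed, because the documents are silent:** an equal daily RRT hazard in both arms; its shape over time; a control in-hospital RRT risk of 0.5% to 5%; stay measured from first dose; discharge unrelated to kidney status.

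**The plan's own figures.** 25% of 152,824,344 euro is 38,206,086 euro, against the stated 38,203,690 (24.998%). The 25% is used consistently, as a cost projection. The sample size also reproduces: (1.960 + 0.842)² × (0.15 × 0.85 + 0.25 × 0.75) / 0.10² = 247.2 per arm, 494 in total, and 494 × 1.05 = 519. It concerns the primary endpoint only and is unaffected by this point.

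**Ratio of counted events with no drug effect.** The ratio is F(9) / F(12), where F(t) is proportional to t for a constant hazard and to 1 − 2^(−t/h) for a hazard that halves every h days.

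| Hazard shape (assumed) | Calculation | Ratio |
|---|---|---|
| Constant | 9 / 12 | 0.75 |
| Halves every 10 days | (1 − 2^−0.9) / (1 − 2^−1.2) | 0.82 |
| Halves every 5 days | (1 − 2^−1.8) / (1 − 2^−2.4) | 0.88 |
| Halves every 3 days | (1 − 2^−3) / (1 − 2^−4) | 0.93 |
| Halves every 2 days | (1 − 2^−4.5) / (1 − 2^−6) | 0.97 |
| Halves every day | (1 − 2^−9) / (1 − 2^−12) | 0.998 |

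The constant-hazard value is the limit for a hazard that does not rise during the stay. At that limit, a true daily hazard ratio of 1 / 0.75 = 1.33 against acetazolamide would show as about 1. Letting stays vary (lognormal, mean 12 days, log-SD 0.4 to 0.8) moves the first three ratios by less than 0.02. With a shortening of 11.7% (the section's lower expenditure figure, borrowed only as an illustration), the constant-hazard ratio is 1 − 0.117 = 0.88.

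**Absolute size, constant hazard.** For control risk c, the daily hazard is λ = −ln(1 − c) / 12 and the acetazolamide risk is 1 − exp(−9λ).

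| Control risk (assumed) | Acetazolamide risk | Expected events, control vs acetazolamide | Difference |
|---|---|---|---|
| 0.5% | 0.375% | 1.30 vs 0.97 | 0.33 |
| 1% | 0.751% | 2.60 vs 1.95 | 0.65 |
| 2% | 1.504% | 5.19 vs 3.90 | 1.29 |
| 5% | 3.774% | 12.98 vs 9.79 | 3.19 |

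The odds ratio is 0.745 to 0.750 across these rows. The chance of a nominally significant difference is roughly 4% to 10%, by a normal approximation that is rough at such counts.

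**With a fixed window**, both arms are counted for the same 90 days and equal hazards give a ratio of 1.00.

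**The case against.** - **RRT is followed to 3 months anyway.** A reader might infer that the acetazolamide arm is watched for fewer days. The documents do not support that. Protocol v2.0 section 9.2 collects RRT as an endpoint event until 3 months after the start dose, SAP section 4.4 has it adjudicated, and section 5.1 requires an estimate, confidence interval and p-value for each exploratory outcome. A later excess would be reported. What remains is narrower: the result filed under safety would still use the discharge-dependent count, while the fixed-window one is framed as a benefit and has no model or analysis set of its own in the SAP.
- **The table may govern.** If so, RRT drops out of the safety endpoint and the window problem with it. The SAP does not say which text prevails, so the contradiction stands first.
- **The 25% is not a firm expectation.** It is a question posed in the economic section, which allows that its estimates may look very optimistic; SAP section 4.1.3 gives no percentage. This affects the size. The direction needs only the stated objective.
- **The bias is not built in.** A reader might infer that acetazolamide looks renally safer by construction. That needs discharge to be unrelated to kidney status. A patient approaching RRT is less likely to be sent home, and a drug that harmed kidneys would tend to lengthen the affected stays. Ultrafiltration or RRT is also an escalation option on the morning of day 3, before 9- and 12-day stays diverge. All of this pulls the ratio towards 1.
- **Creatinine and eGFR are barely touched.** Protocol section 7.9 schedules these tests at screening, days 2 to 4 and 3 months, with none at discharge. This stands: the window problem belongs to the RRT part.

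**Conclusion.** The point holds in a limited form. Section 4.1.4 contradicts itself on the renal safety endpoint; that needs no assumption. Under its definition, the RRT part is counted over a period that treatment is hypothesised to shorten, with no adjustment for time at risk, so the count can favour acetazolamide. The ratios of 0.75 to 0.93 rest on 12 versus 9 days and on assumed hazard shapes, with discharge independent of renal status. More front-loaded events or a smaller reduction in stay bring the ratio closer to 1. In events, the effect is a fraction of one to about three. It is a directional error in the estimate for a rare harm, not a likely source of false significance, and it leaves the primary analysis alone.

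**What to change.** Reconcile the table and the definition in SAP section 4.1.4 into one renal safety endpoint; editing only the definition would leave the table contradicting it.

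- Keep the creatinine and eGFR criteria on days 1 to 4, with the table's thresholds stated in the definition.
- Count RRT over one fixed window from first dose, identical for every patient whether or not discharged. The 3-month period already collected and adjudicated would serve, written as 90 days because the follow-up visit has a +14-day allowance.
- Show the index-stay RRT count descriptively only.

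The cost is a few lines of SAP text, with no new data. The downside is that a 3-month window admits later events less closely tied to a short drug course, which can dilute an early harm, and death competes over that period. Early RRT events should therefore be tabulated by arm alongside the 90-day result.

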7.7 Treatment phase assessments

7.7.1 Day 1

- Request patient to empty their bladder before administration of the first dose of loop diuretics.
- Administer the first bolus of loop diuretics and acetazolamide or placebo to the patient.
- Start the urinary collection immediately after first bolus of loop diuretics and acetazolamide or placebo is administered. The collection will stop the latest as close to but prior to the morning bolus of study medication on day 3. Urinary catheter insertion is strongly recommended but not mandatory to achieve an optimal urine collection. However, in case of urinary incontinence, placement of a urinary catheter is mandatory. Care should be taken to ensure ALL urine is collected. For more details regarding the study urinary collection see [appendix 4](#).

If the patient is enrolled between midnight and 6 a.m., day 1 assessments and day 2 assessment can be performed on the same day but only if there is a difference of minimum 6 hours between the start of the study medication on day 1 and study medication on day 2.

7.7.2 Day 2, Day 3 and Day 4

- Collect vital signs including body weight, arterial blood pressure, heart rate
- As long as patient is assessed as volume overloaded during the previous volume assessment, perform volume assessment by the Principal Investigator or a Sub-investigator who has been trained in the study volume assessment (Figure 3 in section 8)
- Collect morning blood sample for local laboratory assessment: serum haemoglobin, haematocrit, electrolytes (Na, K, Cl, HCO₃), serum urea, serum Cr, serum albumin.
- On the morning of Day 2 and Day 3, collect an urine sample from urine collection period 1 and period 2 respectively for analysis in local lab. In case patient is participating in the optional laboratory sub-study, collect an additional urine sample for each urine collection period for shipment to the University Biobank Limburg for storage and additional research (see [section 7.10](#)). Urinary collection will stop at the morning of day 3 ([appendix 4](#)).
- In case patient is still volume overloaded continue study treatment as described in [section 8](#)
- Collect concomitant medication ([see Appendix 5](#))
- Document and assess adverse events ([section 9](#))
- In addition, on the morning of day 4 or at discharge (whatever comes first):
 - EQ-5D to be completed by the patient.

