4.3.1 STOP TREATMENT

The treating physician is allowed (but not obliged) to stop the study treatment, in case of persistent volume-overload in following cases:

- symptomatic hypotension with a systolic blood pressure <100 mmHg
- asymptomatic hypotension with a systolic blood pressure <90 mmHg
- an increase of serum Creatinine levels x 1.5 of the serum Creatinine level compared to admission value
- occurrence of metabolic acidosis (pH < 7.2)

The discontinuation of the study treatment will be seen as a failure for the primary endpoint (decongestion not achieved). However, if any of these events occur when the patient is judged to be euvolemic, the study treatment is stopped and the primary endpoint is considered to be successful (decongestion achieved).

Freedom from volume-overload (i.e. successful decongestion) on the morning of day 4 will be defined as not more than trace oedema, no residual pleural effusion, and no residual ascites (Figure 2).

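### A patient whose study treatment is stopped for low blood pressure, rising creatinine or acidosis can be scored event-free in the SAP safety analysis, which tabulates neither stops nor adverse events

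*Combined protocol and SAP*

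**What the plan says.** **Endpoints (SAP v2.0, 4.1.4).** Blood pressure: "Hypotension: a value of systolic blood pressure < 85 mmHg at any time during study treatment (day 1- day 4". Acidosis: "Severe metabolic acidosis: a value of bicarbonate < 12 mmol/L at any time during study treatment (day 1- day 4". Renal: creatinine at least doubled or eGFR down by at least 50%; the definition below the table adds need for renal replacement therapy during the index stay. Potassium: 3.0 mmol/L or lower.

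**Stop criteria (SAP v2.0, 4.3.1; same list in Protocol v2.0, 8.1).** The physician may, but need not, stop study treatment for "symptomatic hypotension with a systolic blood pressure <100 mmHg", "asymptomatic hypotension with a systolic blood pressure <90 mmHg", creatinine at 1.5 times the admission value, or "occurrence of metabolic acidosis (pH < 7.2". A stop while volume overload persists counts as a primary-endpoint failure. If the patient is euvolaemic at that moment, the primary endpoint counts as a success.

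**Analysis (SAP v2.0, 5.12).** "The safety outcomes are all binary outcomes". Each is compared by arm in a logistic mixed model in the safety population. No other safety analysis is described.

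**Schedule (Protocol v2.0).** For days 2, 3 and 4, section 7.7.2 asks sites to "Collect vital signs including body weight, arterial blood pressure, heart rate". The procedures table (7.9) places vital signs at screening, on those three mornings and at 3 months, with nothing under day 1. The laboratory lists contain bicarbonate and creatinine but not pH.

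**Other data collected (Protocol v2.0).** The trial summary names adverse events as a safety assessment. Section 9.2 collects all serious adverse events, and non-serious ones that are drug-related, cardiovascular, or involve potassium, sodium or bicarbonate. Section 7.11 requires the reason for discontinuation in the case report form.

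**The concern.** A stop under 4.3.1 shows that the treating physician judged a fall in pressure, a creatinine rise or an acidosis serious enough to withdraw the study drug. If the endpoint for the same harm needs a more extreme value, or a different measurement, that patient need not be counted. Stopping also makes the more extreme value less likely, so the endpoint tends to lose the patients in whom the physician acted.

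If more patients in one arm were stopped for these reasons, the analysis in 5.12 could show no difference. Adverse event records and stop reasons could reveal the imbalance, but the SAP does not use them. The protocol has no data safety monitoring committee, so the end-of-trial comparison of these harms matters the more.

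**Working it through.** The plan gives no calculated figure for the safety endpoints, so there is none to reproduce. The check sets the two sections side by side and measures the gap.

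| Harm | Stop permitted (4.3.1) | Endpoint (4.1.4) | Relation |
|---|---|---|---|
| Low pressure, symptoms | SBP < 100 | SBP < 85 | endpoint further out |
| Low pressure, no symptoms | SBP < 90 | SBP < 85 | endpoint further out |
| Creatinine | 1.5 x admission | at least 2 x baseline, or eGFR down at least 50% | endpoint further out |
| Acidosis | pH < 7.2 | bicarbonate < 12 mmol/L | different measures |
| Potassium | none | 3.0 mmol/L or lower | no comparison possible |

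**Hypotension.** The gap is 100 − 85 = 15 mmHg with symptoms and 90 − 85 = 5 mmHg without. A patient stopped at 95 mmHg with symptoms, or at 87 mmHg without, has no hypotension event unless a lower value is recorded at another time.

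**Creatinine.** Assume that the admission value equals the SAP baseline and that eGFR varies as creatinine to the power −k, with k from 1.0 to 1.25 (my assumption).
- eGFR fall at a 1.5-fold rise: 1 − 1.5^(−k) = 33% (k = 1.0) to 40% (k = 1.25).
- Rise needed for a 50% fall: 2^(1/k) = 2.0-fold (k = 1.0) to 1.74-fold (k = 1.25).

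Over this range of k, a stop at 1.5-fold to about 1.74-fold is not an event on creatinine or eGFR. It would count only if renal replacement followed or the value rose further.

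**Acidosis.** Assume the Henderson-Hasselbalch relation with pK 6.1 and solubility 0.03: bicarbonate = 0.03 x pCO2 x 10^(pH − 6.1). At pH 7.2:

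| pCO2 (mmHg) | 25 | 30 | 35 | 40 |
|---|---|---|---|---|
| Bicarbonate (mmol/L) | 9.4 | 11.3 | 13.2 | 15.1 |

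The crossover is at pCO2 = 12 / (0.03 x 10^1.1) = 31.8 mmHg, or 31.0 with solubility 0.0307. Above it, a patient stopped at a pH just under 7.2 can have bicarbonate of 12 or more and be missed. Below it, bicarbonate falls under 12 before pH reaches 7.2, and the endpoint is the wider of the two. The documents give no pCO2.

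**Readings.** Three pressures are scheduled after treatment starts, over about 72 hours. If only these counted, were 24 hours apart, and episodes began at random, an episode of d hours would include a reading with probability d/24: 8% for 2 h, 17% for 4 h, 25% for 6 h, 50% for 12 h. This is illustrative only, because the any-time wording in 4.1.4 does not say whether unscheduled readings count.

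**Is the gap filled elsewhere in the SAP?** Protocol v2.0, 3.6 lists milder outcomes: acidosis needing bicarbonate supplements, hypokalaemia, and worsening renal function (creatinine up more than 0.3 mg/dL or eGFR down more than 20%). The last would capture a 1.5-fold creatinine rise on the calculation above. None of the three appears in the exploratory list of SAP 4.1.5.

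**The case against.** The strongest reply is that a permissive stop trigger and a severe-event endpoint serve different purposes, so different thresholds are not in themselves a contradiction. That stands, and it is why the endpoints should stay as they are. It does not explain why stops and adverse events are left out of the analysis.

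Second, stops are not ignored, because under persistent overload they count as primary failures. This is true, but there they merge with every other kind of failure and the reason is lost. A stop in a euvolaemic patient counts as a success.

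Third, the SAP limits its stated scope to the primary and secondary objectives and commits to CONSORT reporting, so adverse events may still be reported. That is fair: a missing table does not prove they will go unreported. The by-arm comparison is nevertheless not prespecified.

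A reader might also infer more than the documents support:
- **That all the safety endpoints lie beyond the stop criteria.** This is shown for two of four. Potassium has no stop criterion, and for acidosis the order depends on pCO2.
- **That these patients have no safety record.** Protocol 9.2 should capture many of them as adverse events; the gap is in the planned analysis.
- **That this is the trial's only safety comparison, or that the table will be nearly empty.** Mortality enters a secondary endpoint, hyponatraemia and renal replacement are exploratory outcomes, and the steering committee reviews safety data. No event rates are given, and a power comparison at assumed rates would show only that commoner events give more power.
- **That only morning pressures count.** The wording of 4.1.4 leaves this open.

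**Conclusion.** The point holds for hypotension and creatinine on the face of the text. The endpoints lie 5 to 15 mmHg below the pressures, and from about 1.74-fold upwards against 1.5-fold for creatinine, at which a stop is already permitted. The creatinine figure rests on the assumed range of k and on equal admission and baseline values. For acidosis the defect is a mismatch of measures: a stopped patient can be missed, under the stated assumptions when pCO2 exceeds about 31 to 32 mmHg.

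In each case the patient can be scored event-free in 5.12, and no planned analysis of stops or adverse events would show it. The number of patients affected cannot be estimated from the documents. The weakness concerns what the trial can conclude about these three harms, not its primary result. It is worth correcting because the correction is cheap.

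**What to change.** Keep the 4.1.4 endpoints and thresholds. In SAP 5.12 add, by arm in the safety population:

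1. The number of patients whose study treatment was stopped, by each 4.3.1 criterion as far as the recorded reasons allow.
2. The number with a hypotension, renal, or acidosis/bicarbonate adverse event or serious adverse event on the eCRF.
3. A supportive per-patient outcome for hypotension, creatinine and acidosis: endpoint value, or stop for that criterion, or matching adverse event.

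In 4.1.4 keep the any-time wording and state that every recorded value counts, scheduled or not. Restricting the endpoint to scheduled morning values would discard unscheduled low readings and enlarge the loss. SAP 4.1.4 and 4.3.1 and Protocol 7.9 and 9.2 should be reconciled on which data feed each endpoint. No stop rule or clinical threshold is changed.

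The cost is SAP wording, settled before unblinding, and a few tables. There are three limits. Protocol 7.11 does not show that reasons are coded to the four criteria. Non-serious renal events are collected only if drug-related or within the other listed categories. The supportive outcome mixes in discretionary stops and milder events, so it belongs beside the existing endpoint and should not replace it.
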